1.1 Previous research on the neoSpotTM product

The neoSpotTM system is a new prototype in the series of vital sign monitors designed by Neopenda. The product is an iteration of the current vital signs monitor, neoGuardTM, which provides continuous measurement of pulse rate (PR), peripheral blood oxygen saturation (SpO₂), respiratory rate (RR) and temperature to patients in tertiary care settings. The neoSpotTM system has been developed to capture instantaneous readings in settings such as community outreaches or lower-level health facilities, where reliable vital sign measurement equipment is not readily accessible. Since the new product will comprise of similar hardware and algorithms to its precursor, neoGuardTM, it is expected to perform at the same level of accuracy for measurement of PR, SpO₂, RR and temperature. Measurement of an additional parameter, blood pressure (BP), is in the early stage of development and will add substantial value to the previous product. The data generated from this study will help in the final integration of BP measurement to the neoSpotTM system. While this will be the first field study on neoSpotTM itself, related research has been conducted on the precursor system, neoGuardTM, as detailed below. Our path to evaluating and developing neoSpotTM into a commercial product will follow a similar pathway.

Table 1. *Research history of Neopenda's wearable vital signs monitors*

Timeline	Location	Device Version	Description	Purpose	Sample Size	Status
Jul 2019	TMC, Boston, MA, USA	neoGuard V1.0	Pilot study	Evaluate and refine signal quality	22 neonates	Complete
Oct 2019	Jinja RRH	neoGuard V2.0	Pilot study	Evaluate preliminary accuracy	27 infants and stable neonates	Complete
Sep 2020	Clinimark Laboratories	neoGuard V3.0	Accuracy study	Validation of final accuracy	15 healthy adults	Complete
Oct 2020	UCSF Hypoxia Lab	neoGuard V3.0	Accuracy study	Validation of final accuracy	15 healthy adults	Complete
Feb 2021	Jinja RRH	neoGuard V3.0	Feasibility study	Evaluate preliminary accuracy	30 adult patients	Complete
Mar-May 2021	Kenya	neoGuard V3.0	Feasibility study	Evaluate feasibility and efficacy	172 neonates	Complete

Mar-May 2022	Nigeria	neoGuard V3.0	Feasibility study	Evaluate feasibility and efficacy	~225 neonates	Ongoing
Apr 2022 – Apr 2023	Kenya	neoGuard V3.0	Interrupted time series study	Evaluate clinical impact and cost-effectiveness	~3,000 neonates	Ongoing

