6.0 Research questions

1. Is the NeoSpot a feasible, acceptable, and easy to use device when used by CHWs during community ANC outreach activities?
2. Can photoplethysmograph (PPG) sensor data from NeoSpot be used to develop an accurate and reliable blood pressure algorithm?

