Study hired Research Assistants (RAs) will approach potential study participants for both study aims and consent them for study participation. Following enrollment, for Aim #1, CHWs and pregnant women will undergo IDIs in a safe and secure location. IDIs will last approximately 1 hour and they will be conducted in the preferred language of the consented study participant. All study participants will exit the study following the IDI. For Aim #2, study staff will measure their vital signs and blood pressure using the NeoSpot, which data will be automatically stored into the smartphone provided by the study. Results of the vital signs and the blood pressure will also be shared with the clinical treatment team following screening. The treating clinicians will notify the patient of the results and, if required, refer the pregnant women for appropriate care according to local standard of care. All study participants under Aim #2 will exit the study following this stage.

Data Collection

All data for Aim #1 will be recorded on a study audio recorder and then translated and transcribed onto a word document by a study team member. Once it is transcribed and has been reviewed for completeness, the audio recording will be destroyed.

For Aim #2, PPG data will be automatically collected and stored by the NeoSpot directly into the smartphone, without the use of data collection tools. It will be stored on smartphones provided to the CHWs by the study. Following data storage, PPG data will be used to develop an accurate and reliable blood pressure algorithm for future piloting. Confidentiality of patient identifiers will be protected by using a patient identification key that will be stored separately from the data set. Each study participant will be assigned a unique study identification number. The database will be password protected, accessible only to the study PI and data analyst.

Data Analysis

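### NeoSpot blood pressure has no stated accuracy and an unfinished algorithm, yet the plan shares it and refers on it with no stated safeguard against a falsely normal value

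*Combined protocol and SAP*

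**What the plan says.** **Status of BP.** Section 1.1 states that "Measurement of an additional parameter, blood pressure (BP), is in the early stage of development". The accuracy carried over from the precursor device, neoGuard, is limited to the parameters neoGuard measures: "it is expected to perform at the same level of accuracy for measurement of PR, SpO₂, RR and temperature". The same section adds that "The data generated from this study will help in the final integration of BP measurement". Research question 2 in section 6.0 asks: can the PPG (photoplethysmograph) "sensor data from NeoSpot be used to develop an accurate and reliable blood pressure algorithm"? Aim 2 in section 7.0 trains a machine learning model on the raw PPG data collected here. Data Collection in section 8.0 says that "PPG data will be used to develop an accurate and reliable blood pressure algorithm for future piloting", and Data Analysis repeats that the pilot comes later.

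**Use of BP.** Study Design in section 8.0 says that algorithms in the device calculate BP and that the data go to the phone app. Study Procedures says that "study staff will measure their vital signs and blood pressure using the NeoSpot", then "Results of the vital signs and the blood pressure will also be shared with the clinical treatment team following screening", and then "The treating clinicians will notify the patient of the results and, if required, refer the pregnant women for appropriate care". Women in Aim 2 leave the study after this stage. Section 9.0 describes BP testing as done with a skin sensor and refers women with abnormal values for further assessment and treatment.

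**Risks and benefit.** Section 9.0 names skin harm and loss of confidentiality as risks. It says there may be no direct benefit, but also sets the detection of danger signs against the risks.

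**The concern.** The plan treats one quantity in two ways. As a research object, NeoSpot BP is unfinished: the study exists partly to supply data for its algorithm. As a clinical result, it is reported and acted on alongside four parameters for which accuracy comparable to the precursor's is expected. A treating clinician who receives all five together is not told, in the procedures, that one of them stands on a different footing.

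The two directions of error are not equally protected. A value that is too high leads to referral and further assessment, which can correct it. A value that is too low looks normal and triggers nothing. A woman with raised BP could then be given a normal NeoSpot value as her BP result, with no stated instruction that it needs confirming. In antenatal care this matters because section 3.0 names eclampsia and pre-eclampsia among the danger signs that the device is meant to help find.

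**Working it through.** The plan gives no BP accuracy figure, error target or precision basis for the 125 women, so there is no figure to reproduce. The check compares the statements.

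**1. Is there a stated accuracy for BP?** Five parameters are measured. Section 1.1 gives an expectation for four of them (pulse rate, SpO₂, respiratory rate, temperature). That expectation cannot extend to BP, because it is inherited from a precursor that is not described as measuring BP. Elsewhere, accuracy and reliability appear only as goals for the algorithm. Study Design places final validation and field testing of the device in the future.

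**2. Does a BP output exist in this study?** The text points both ways.
- *For:* Study Design has the device calculating and transmitting BP and puts the device as a whole in its final stages of development. Section 1.1 speaks of final integration of BP, and Data Analysis speaks of developing the algorithm further.
- *Against:* section 1.1 puts BP at an early stage, section 6.0 poses the algorithm as an open question, and section 7.0 trains the model on data still to be collected.

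No statement settles this. A preliminary output is plausible but not certain.

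**3. What follows from each error, as written?**

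| NeoSpot BP | Action stated | Error corrected? |
|---|---|---|
| Falsely high | Referral for further assessment (section 9.0) | Yes, at that assessment |
| Falsely normal | None stated | No |

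The extra testing mentioned in section 9.0 applies once a danger sign has been found, so it does not reach the second row. No cuff or other BP source is named in the procedures.

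**4. Is routine measurement a backstop?** Section 2.0 describes intermittent manual measurement of vital signs or BP at most antenatal clinics in such settings. Section 1.0 says most antenatal clinics do not monitor BP. On these two accounts the backstop is uncertain.

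**5. Exposure.** Women whose NeoSpot BP would be returned: up to 125 if an output exists, 0 if none does. Each percentage point of participants with a falsely normal value is 125 × 0.01 = 1.25 women.

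**6. Illustration only.** The expected number of falsely normal readings is 125 × prevalence × (1 − sensitivity). The documents give neither input. Assuming prevalence of raised BP from 5% to 15% and sensitivity from 50% to 90%:
- lowest: 125 × 0.05 × 0.10 = 0.6 women
- middle (10%, 70%): 125 × 0.10 × 0.30 = 3.75 women
- highest: 125 × 0.15 × 0.50 = 9.4 women

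These figures show that even a modest miss rate could touch a few women. They do not estimate harm, because they take no account of what would have happened without the device.

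**The case against.** The strongest reply has four parts.

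**The status is disclosed.** Section 1.1 calls BP early-stage, section 7.0 calls NeoSpot a prototype, and sections 7.0 and 8.0 call it a test device. This stands: a reader might infer that the protocol hides the experimental nature of BP, and it does not. What is missing is that caveat at the point where results are shared and acted on.

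**A clinician stands between the device and the woman.** Results go to treating clinicians, who work to the local standard of care. Nothing says NeoSpot replaces a routine BP reading, and leaving a single-contact study is not leaving antenatal care. This stands as mitigation. It does not close the gap, because the clinicians are not told to treat the value differently from the other four.

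**The warning may be elsewhere.** Staff discuss procedures, risks and benefits before consent, and CHWs are trained on the device. The consent pages and two section 8.0 figures were not available for this review. A warning there cannot be excluded. The procedures and section 9.0 were available, and neither carries one.

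**A reading may be better than none.** If most clinics do not monitor BP, some women would otherwise have no value at all. This also stands, and it is why net harm cannot be claimed. It does not justify presenting a normal value without qualification.

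On benefit, the danger signs in section 9.0 are not specific to BP, and the other four parameters can reveal some of them. Only the BP share of that benefit lacks a stated accuracy basis.

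**Conclusion.** The concern holds and should be fixed. As written, the procedures and section 9.0 put a BP value of unstated accuracy into care, with protection against a false high and none stated against a false normal. Exposure is up to 125 women, conditional on a BP output existing. If none exists, the harm from false reassurance is zero and the fault is one of consistency: sections 8.0 and 9.0 promise a result that cannot be delivered.

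Three stronger readings are tempting but unsupported:
- *That NeoSpot BP is inaccurate.* Its accuracy is unstated, not shown to be poor.
- *That women would be worse off than under current practice.* The documents give no BP error and no prevalence of raised BP, and they describe current practice in two different ways.
- *That the study cannot proceed until this is resolved.* That would need evidence on the first two points.

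The conclusion rests on the protocol text without its consent pages and figures, and applies to BP only.

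**What to change.** 1. In Study Design (section 8.0), state whether a BP output is displayed in this study.
2. If it is, amend Study Procedures and section 9.0 so that:
   - the value is marked investigational wherever it is shown or shared, including the CHW's app;
   - a normal NeoSpot BP is not reported as a completed BP check and does not replace standard-of-care measurement;
   - a high NeoSpot BP only prompts referral for a standard-of-care BP;
   - no treatment decision rests on the NeoSpot value.
3. If no output exists, delete BP from the results returned under Study Procedures and from the referral sentence in section 9.0.
4. In section 9.0, add BP measurement error (false reassurance and false alarm) to the risks, and do not count BP toward the danger-sign benefit.

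The other four parameters are shared as now. A cuff reading for every woman would give stronger protection, but it is not needed to remove the unqualified reliance described here.

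**Cost.** One protocol amendment, a label, a line in CHW and staff training, some extra referrals from false highs, and a less favourable stated benefit. True highs still reach assessment. The Aim 1 interviews can still cover the BP readout if there is one.

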9.0 Ethical considerations

There will be no obligation to participate in the study, and informed consent will be obtained from each participant who chooses to enroll. There is minimal risk for patients

included in this study. Vital signs and blood pressure testing is non-invasive, and achieved by placing a sensor on the skin. In this study, the NeoSpot device will be in place on the skin for <1 minute making the risk for harm to the skin very low. Pregnant women with abnormal vital signs and blood pressure will be referred for further clinical assessment and treatment, which will be provided by the health facility at no cost to the family. The risk of these outcomes is balanced by the benefit of detecting danger signs in a pregnant women during ANC community outreach activities.

We will work hard to protect personal and health information collected in the study as described above. Like all studies there is a small risk that personal or health information could become known to others and this could cause harm to the study participants. To prevent this, research records will be kept confidential in a lockable cabinet to the maximum extent permitted by law. There may be no direct benefit to study participants. In the case that a danger sign, a benefit will be that we can communicate this finding with the pregnant woman's healthcare provider so that she can receive appropriate treatment and additional testing if needed.

The study protocol will undergo review and approval by local (UNZA-BREC, NHRA, and ZAMRA) and international (University of Alabama at Birmingham IRB) regulatory authorities. There are no direct costs to study participants. Participants will receive compensation for their time in the form of cash valued at 100 ZMK.

